7.1.1 Safety

Any solicited or non-solicited ocular or systemic adverse events (AEs) from all participants will be utilized to summarize safety data for this phase I/II study. Reported AEs will be subdivided into pre-treatment and post-treatment, where post-treatment is defined as those occurring on or after the day of the first treatment (cellular or sham). AEs will be summarized by presenting the number of events, and also by counts and frequencies for the number of participants with AEs, and the severity and relatedness of each AE to study treatment (i.e., CD34+ cells) or study procedures (i.e., intravitreal injection). Summaries will be broken down by the treatment period in which the AE occurred (Treatment Period 1, Treatment Period 2). Summaries of events in the study eye will also be provided. Detailed listings of post-treatment AEs and pre-treatment AEs will be provided.

All AEs will be coded using MedDRA[®] dictionary version 21.0 or higher. Post-treatment AE incidence rates will be summarized by System Organ Class (SOC) and Preferred Term (PT) as determined by the MedDRA coding, with summaries broken down by the treatment period in which the AE occurred. Summaries of MedDRA coded events in the study eye and fellow eye as well as non-ocular AEs will also be provided. The incidence rate of an AE is calculated as the number of participants who experience the event at least once during the safety window divided by the number of participants at risk (times 100). Incidence rates will be calculated at the PT level, at the SOC level, and for participants with at least one post-treatment AE. If a participant experiences multiple episodes of an event, then the event is only counted once. Fisher's exact test may be performed to compare incidence rates between the two treatment arms.

Post-treatment Serious Adverse Events (SAEs) will be summarized by presenting the number of events, and also by counts and frequencies for the number of participants with post-treatment SAEs, and the relatedness and type of each SAE, broken down by whether the SAE occurred in Treatment Period 1 or Treatment Period 2. A summary of post-treatment MedDRA-coded SAEs

using incidence rates will be provided if enough events have occurred. Incidence rates, as defined above, will be calculated at the PT level, at the SOC level, and for "At Least One Serious Adverse Event." Detailed listings of post-treatment SAEs and pre-treatment SAEs will be provided.

The primary safety outcome will be assessed at the end of Treatment Period 1 (at approximately month 6). Adverse events that occur during Treatment Period 1 will be broken down by whether the AE occurred following the sham or cellular treatment to assess differences in the adverse event experience between the cellular and sham therapies.

A participant listing of the number of study eye, fellow eye and non-ocular AEs will be provided broken down into 3 time periods (0-6 months following sham therapy, 0-6 months following cellular therapy and 6-12 months following cellular therapy) sorted by number of CD34+ cells injected and treatment arm to examine whether more AEs may be observed in those participants who received more CD34+ cells.

In order to assess whether there are any trends in when adverse events are reported, we will also present adverse events based on the how much time has elapsed from receipt of sham and cellular therapy. Depending on how many events are reported, we may create categories (e.g., events reported between 0- and 1-month post-therapy, events reported between 1 and 6 months, events reported between 6 and 12 months, etc.). In this analysis, data will be collapsed over both treatment arms, and will be summarized for all AEs and study eye AEs.

Summaries and listings of solicited ocular events in the study eye and in the fellow eye will be provided, broken down by treatment arm and visit. In addition, a summary of vision-related events broken down by Treatment Period will be provided in an attempt to combine information about unsolicited and solicited ocular events in a single table. Unsolicited ocular events such as reduced visual acuity and visual impairment and solicited ocular events such as decreased vision and blurred vision will be considered for inclusion.

Events related to bone marrow or sham aspiration will be summarized. In addition, pre-treatment AEs will be provided in a listing.

A summary of post-injection vision and eye examination will be provided, broken down by Treatment Period and will include a summary of intraocular pressure (IOP), any IOP interventions administered, and any changes or symptoms seen following injection.

7.1.2 Feasibility

The number and percent of study participants undergoing successful bone marrow aspiration will be summarized. The mean and range of volume of bone marrow aspirate, number of CD34+ cells isolated and number of CD34+ cells injected intravitreally will be described to determine whether a desired number of stem cells can be isolated from bone marrow aspiration without sedation in an outpatient setting. Any participant who did not tolerate the bone marrow aspiration without sedation without sedation and any unsuccessful bone marrow aspiration attempt will be recorded.

Other pre- and post-release analysis parameters such as percent yield of the CD34+ isolation will also be described.

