the CD34+ cells from the mononuclear cell fraction. There will be no genetic research testing performed. The isolated CD34+ cells will be washed, subjected to stat sterility assays (including endotoxin assay and gram stain), and stat viability testing with trypan blue staining and resuspended in 0.15 cc volume of BSS Plus. The final stem cell product (0.1 cc containing at least 800,000 viable nucleated CD34+ cells (where the cell count is based on the Miltenyi CliniMACS cell sorting process as noted above) will be sent to the Eye Center in a 1 ml tuberculin syringe for intravitreal injection. The remaining 0.05 cc of the final stem cell product will be used for post-release analysis to characterize the final stem cell product. This will include flow cytometry for CD34 and CD3 content and 7-AAD viability testing. Additional analysis for potency and characterization of the final product will be performed. These additional analyses will include flow cytometric panel analysis for hematopoietic stem cells that are CD133(+)/CD45(+)/CD34(+) versus angiogenic cells (i.e., endothelial progenitor cells) that are CD31(+)/VEGFR-2(+)/CD45(-)/CD34(+). In addition, the post release flow cytometry panel will include analysis of CD34+ cells with VEGF receptor-2 (VEGFR-2), namely VEGFR-2+/CD34+, as well as, % CD133(+); % CD31(+); % CD45(+); % VEGFR-2 (+).

On the morning of the study procedure, ETDRS VA is performed prior to the aspiration procedure and study injection. In addition, the unmasked treating ophthalmologist will perform a complete eye exam including fundus examination and a slit lamp examination of the study eye to ensure there are no new changes from baseline. This is done prior to study injection. The isolated CD34+ cells will be injected intravitreally by the unmasked treating ophthalmologist (retinal specialist) under local anesthesia. The intravitreal injection will be performed within two hours and on the same day following release of the final stem cell product from the GMP laboratory.

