will be performed to ensure that the central retinal artery is perfused and to ensure that there are no complications associated with the injection. Intraocular pressure (IOP) will be measured after injection. If the vision is hand motions or light perception and IOP is > 40 mm Hg, glaucoma medications will be started to lower IOP. If the vision is no light perception and IOP is > 40 mm Hg, a paracentesis will be performed after reapplying 2 to 3 drops of 5% povidine-iodine solution and opening the eyelid with a sterile lid speculum. A 30g needle attached to a 1 mL syringe will be used to remove a maximum of 1 mL of aqueous from the anterior chamber. The lid speculum will be removed and visual acuity of at least counting fingers will be confirmed. Indirect ophthalmoscopy will be performed to confirm perfusion of the central retinal artery.

Following stem cell injection or sham injection, a complete eye examination will be performed to ensure there is no new change after the injection. This will include a slit lamp examination which will check for hyphema or cells visible in the anterior vitreous. Then, the eye will be washed with balanced saline solution, followed by application of antibiotic eye drop and erythromycin or similar antibiotic eye ointment. Then, the eye examination chair will be reclined to allow the participant to be in the supine position for 30 minutes. Thereafter, the participant will be discharged and instructed to use topical antibiotic drops four times a day in the injected eye for one week. The number of viable nucleated CD34+ cells to be injected per eye will be recorded and will range from 800,000 to 10 million, depending on the yield of the bone marrow aspiration and the isolation procedure and where the cell count is based on the Miltenyi CliniMACS cell sorting process. The percent viability of the cells as noted pre-release using trypan blue staining by the GMP laboratory will also be recorded. Any irregularity in size or shape of the cells in the final product as noted by the GMP laboratory staff will also be recorded.

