6.3 Outcome Measures

6.3.1 Primary Safety and Feasibility Outcome Measures

The primary outcome measures for the safety and feasibility of the stem cell therapy are the following:

- Incidence and severity of ocular and systemic adverse events reported during Study Period 1 (i.e., the day of the first treatment (Treatment 1) up to but not including the day of the second treatment (Treatment 2)
- The mean and range of number of CD34+ cells isolated from the bone marrow aspirate and the number injected into the eye

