7.3 Study Treatment

Bone marrow aspiration, CD34+ stem cell isolation and intravitreal administration will be performed using sterile techniques. All three procedures will be done on the same day to maximize viability of the isolated cells. Similarly, the corresponding sham bone marrow aspiration and sham injection will be administered within the same day. The number of viable nucleated CD34+ cells to be injected in the eye will vary from 800,000 to 10 million cells per eye, depending on the volume of the marrow aspirated and the efficiency of the stem cell isolation procedure, where the cell count is based on the Miltenyi CliniMACS cell sorting process. On average, we anticipate injecting about one million CD34+ stem cells per eye in a volume of 0.1 ml.²³

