7.6 Participant Discontinuation/Replacement

Participants have a right to withdraw from the study at any time and for any reason. The Enrollment Center may request to withdraw a participant because of protocol deviation, administrative reasons, safety concerns, inadequate number of viable nucleated CD34+ cells harvested for intravitreal injection (where the cell count is based on the Miltenyi CliniMACS cell sorting process) or any other valid and ethical reasons. A study termination form will be completed citing the reason for the termination. In the event that a participant is terminated from the study

after randomization and prior to receipt of treatment (cellular or sham) at the Treatment 1 visit regardless of the reason, an additional participant will be accrued as a replacement. In the event that a participant receives the first treatment but opts not to receive the second treatment, an additional participant will be accrued as a replacement, but the original participant will be encouraged to return for all study visits to ensure the participant's safety is not compromised. The replacement participant will receive both treatments and will be followed for 12 months, the same as any other participant enrolled in the study. If a participant is terminated or withdraws from the study following the receipt of the second treatment, the participant will again be encouraged to return for all study visits for safety monitoring but will not be replaced. A maximum of one participant may be replaced, regardless of timing of withdrawal. If a participant terminates the study due to having less than 800,000 viable nucleated CD34+ cells (where the cell count is based on the Miltenyi CliniMACS cell sorting process) in the final product for intravitreal injection, the participant will have the option to receive the harvested cells as part of the on-going open-label pilot study provided that the harvested cells pass the release criteria for quality and sterility.

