
2.0 STUDY OBJECTIVES

2.1 Primary Objective

The primary objective of the study is to assess the safety and feasibility of the stem cell therapy, which will be evaluated using the following primary outcome measures:

- Primary safety outcome: Incidence and severity of ocular and systemic adverse events reported during Treatment Period 1 (i.e., the day of the first treatment (Treatment 1) up to but not including the day of the second treatment (Treatment 2)).
- Feasibility outcome: The mean and range of number of CD34+ cells isolated from the bone marrow aspirate and number injected into the eye.
- Secondary safety outcome: Incidence and severity of ocular and systemic adverse events reported throughout study duration.

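### The feasibility outcome does not directly answer whether enough cells can be obtained: the planned success percentage is not tied to the 800,000 minimum, and the modified ITT rule drops harvest failures at Treatment 1 but keeps those at Treatment 2

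*SAP*

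**What the plan says.** **The outcome.** Protocol 6.3.1 defines feasibility as "The mean and range of number of CD34+ cells isolated from the bone marrow aspirate and the number injected into the eye". SAP 2.1 repeats this almost word for word: "The mean and range of number of CD34+ cells isolated from the bone marrow aspirate and number injected into the eye". Neither definition contains a proportion.

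**The purpose.** SAP 7.1.2 says that these summaries "will be described to determine whether a desired number of stem cells can be isolated". That section gives the desired number no value.

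**The proportion that is planned.** SAP 7.1.2 and Protocol 7.8.2.1 add a count and percentage of participants with a successful aspiration. SAP 7.1.2 also has unsuccessful attempts recorded. Success is not defined, no cell count is attached to it, and no interval is planned.

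**The minimum.** Protocol 6.1.5 describes the final product as "0.1 cc containing at least 800,000 viable nucleated CD34+ cells" and says that the number injected "will range from 800,000 to 10 million, depending on the yield of the bone marrow aspiration". Protocol 7.6 covers the shortfall: "If a participant terminates the study due to having less than 800,000 viable nucleated CD34+ cells", the participant may receive the cells in the separate open-label pilot, provided that they pass release criteria for quality and sterility.

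**The population.** SAP 4.3 puts all analyses other than safety on the ITT population, and SAP 4.1.2 restricts that to randomized participants who received the first injection. SAP section 11 labels both feasibility outputs ITT. SAP Table 2 excludes an inadequate sample before Day 0 treatment (scenario 1) and includes one in Period 2 (scenario 3).

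**The concern.** Whether enough cells can be obtained is a yes-or-no question for each aspiration. Its natural summary is the share of aspirations that reach the limit.

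The number injected cannot supply that share. Values below 800,000 are removed by rule, so the minimum cannot show failure, and losing the poor harvests raises the mean. The number isolated has no such floor, but its minimum shows only that one harvest was low, not how many were. It is also a different quantity from the dose: the cells are "resuspended in 0.15 cc volume of BSS Plus" and 0.1 cc of that is injected.

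The planned percentage could fill the gap, but two things are unsettled. First, an aspiration could count as successful because marrow was drawn and the procedure tolerated, even if the product fell short. Second, the population rule treats the same event differently according to when it occurs. Treatment 1 harvests belong to the immediate-cell arm and Treatment 2 harvests to the deferred-cell arm, so the omission falls on one arm only.

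Feasibility is part of the primary objective. A later trial would need the probability that one aspiration gives an injectable product.

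**Working it through.** The plan states no success rate, target or precision for feasibility, so there is no figure of its own to reproduce.

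**Inputs from the documents.** 20 participants randomized 1:1, so 10 per arm, each scheduled for one real aspiration (SAP 3.2, 3.3); minimum 800,000 (Protocol 6.1.5, 7.6); at most one replacement (SAP 3.6). **Assumed:** a 95% two-sided confidence level, and the yield distributions in steps 2 and 3.

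**Step 1. Effect of the population rule.** Suppose two harvests fail in each arm and, for simplicity, nobody is replaced.

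| Denominator | Immediate cell | Deferred cell | Overall |
|---|---|---|---|
| All real aspirations begun | 8/10 = 80% | 8/10 = 80% | 16/20 = 80% |
| Modified ITT | 8/8 = 100% | 8/10 = 80% | 16/18 = 88.9% |

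The overall figure rises by 8.9 percentage points, and a 20-point difference between arms appears that does not exist. The same two Treatment 1 harvests also leave the counts of cells isolated.

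**Step 2. Whether the mean injected identifies the success rate.** Assume log-normal yields, injected only if at least 0.8 million. With log-SD s and success rate P, the log-median is ln(0.8) + s·Φ⁻¹(P). The mean injected is exp(log-median + s²/2) · Φ(Φ⁻¹(P) + s)/P. Fixing it at an assumed 1.2 million and solving for s gives:

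| Success rate P | s | Mean of all harvests (million) | Mean injected (million) |
|---|---|---|---|
| 50% | 0.46 | 0.89 | 1.2 |
| 70% | 0.36 | 1.03 | 1.2 |
| 80% | 0.32 | 1.10 | 1.2 |
| 90% | 0.26 | 1.15 | 1.2 |
| 95% | 0.22 | 1.18 | 1.2 |

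The same mean injected fits success rates from 50% to 95%.

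**Step 3. What share might fall below the minimum.** Assume a log-normal yield with mean 1.0 million over all harvests and coefficient of variation c. Then s² = ln(1 + c²), z = (ln 0.8 + s²/2)/s, the share below is Φ(z), and the mean among those injected is Φ(s − z)/(1 − Φ(z)).

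| c | s | z | Share below 0.8 million | Mean injected (million) |
|---|---|---|---|---|
| 10% | 0.100 | −2.19 | 1.4% | 1.00 |
| 15% | 0.149 | −1.42 | 7.8% | 1.02 |
| 20% | 0.198 | −1.03 | 15.2% | 1.05 |
| 30% | 0.294 | −0.61 | 27.0% | 1.12 |
| 50% | 0.472 | −0.24 | 40.7% | 1.28 |

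The documents give no value of c, so this is a range and not a prediction. As the share of failures rises, so does the mean injected.

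**Step 4. Precision of the proportion.** Exact (Clopper–Pearson) 95% limits for x successes in n are the 2.5% quantile of Beta(x, n − x + 1) and the 97.5% quantile of Beta(x + 1, n − x). For 20/20 the lower limit is 0.025^(1/20) = 0.832.

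| x/n | Percent | Exact 95% CI |
|---|---|---|
| 20/20 | 100% | 83.2–100% |
| 18/20 | 90% | 68.3–98.8% |
| 16/20 | 80% | 56.3–94.3% |
| 20/21 (one failure, replaced) | 95.2% | 76.2–99.9% |

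Even 20/20 is compatible with a failure rate of up to 16.8%.

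**The case against.** A fair opponent would say that the plan already holds most of what is needed. SAP 7.1.2 plans a success percentage and records unsuccessful attempts. The number isolated has no floor. SAP 7.1.3 tabulates each participant's total CD34+ count in the marrow, and pre- and post-release parameters are listed. Protocol 7.6 requires a termination form that states the reason, and a CONSORT diagram is planned. With about 20 participants and one replacement at most, many failures would also show as missing treated participants. All of this stands. A reader might infer that the plan cannot show how often a usable product is obtained, or that failed harvests would go unseen. The documents do not support that. However, SAP section 11 labels the clotting table, the product listing and the early-termination summary ITT, so under Table 2 a Treatment 1 failure falls outside them. The CONSORT diagram is not restricted in this way.

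A second tempting inference is that 15% to 41% of harvests will fail, because the expected one million is only 25% above the minimum. This does not hold either. Protocol 7.3 says "On average, we anticipate injecting about one million CD34+ stem cells per eye", which is a mean of cells injected and so already conditional on the minimum. The coefficients of variation behind those percentages are assumptions, and a value of 10% gives 1.4%. Protocol 4.0 reports that in the pilot the desired number was obtained from a single aspirate in each participant.

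Third, the SAP is descriptive, and no decision rests on an interval. That is true, and any reader can compute one from x/n, provided that x and n are defined.

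**Conclusion.** The point holds in a limited form. The defined outcome does not directly answer the question that SAP 7.1.2 sets. The planned percentage could answer it, but success is not tied to the 800,000 minimum, and the ITT rule omits failures at one treatment visit while keeping them at the other. Followed as written, the plan can overstate feasibility and create a difference between arms.

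The size depends on how many harvests fail at Treatment 1. With none, the population rule causes no bias. In the example of two failures per arm, the overall rate moves from 80% to 89%. That example rests on assumed failures, a literal reading of SAP 4.3 and Table 2, and no replacement. The documents do not allow the true failure rate to be estimated.

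This should be changed before analysis. It goes beyond a missing detail because the denominator affects the result, but it does not undermine the trial.

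**What to change.** In SAP 7.1.2:

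1. Define success as a final product that meets the protocol's existing minimum of 800,000 viable nucleated CD34+ cells. Report any failure of the quality or sterility release criteria separately, so that yield and release failures are not mixed.
2. Take as denominator all participants in whom a real bone marrow aspiration was begun at Treatment 1 or Treatment 2, including those not injected or later replaced. State that this replaces ITT for the feasibility outputs, and change their population label in SAP section 11.
3. Report x/n with an exact 95% CI, beside the mean and range of cells isolated for all attempts.
4. Label the number injected as conditional on meeting the minimum.

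The cost is some SAP wording and one table line. The changes use the protocol's own limit and alter no clinical procedure. The downside is that the feasibility figure may look slightly less favourable.

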7.1.3 Supportive Analysis for Primary Outcome

The measures collected as supportive analysis measures for the primary outcome include presence of clotting in the bone marrow aspirate, information collected regarding COVID-19 symptoms, testing and exposure, occurrence of pregnancy, and concomitant medications. Clotting data will be presented as a summary for each participant noting their number of CD34+ cells in total bone marrow, the number of syringes used to collect the aspirate and whether there was clotting present in any of the syringes. The COVID-19 questions were added to the data system in August 2020 and each response to each question will be presented in summary format

in counts and percentages. Any pregnancies will be presented in a listing. Each concomitant medication will be summarized by noting the indication(s) for which it was taken, number of participants who reported taking the medication, number of times reported being taken, and the mean number of days taken. Concomitant medications will also be presented in a listing.

